3.3 Inclusion of Women and Minorities

The study is open anyone regardless of gender or race/ethnicity. Efforts will be made to extend the accrual to a representative population. However, a balance must be struck between subject safety considerations and limitations on the number of individuals exposed to potentially toxic or ineffective treatments on the one hand and the need to explore gender, racial, and ethnic aspects of clinical research on the other. If differences in outcome that correlate to gender, racial, or ethnic identity are noted, accrual may be expanded or additional studies may be performed to investigate those differences more fully.

4.0 SCREENING AND REGISTRATION PROCEDURES

4.1 Screening Procedures

Diagnostic or laboratory studies performed exclusively to determine eligibility for this trial will be done only after obtaining written informed consent. Studies or procedures that were for clinical indications (not exclusively to determine study eligibility) may be used for baseline values, even if the studies were done before informed consent was obtained. All screening procedures and their respective windows are detailed in [Section 10, Table 10, Study Activity Calendar](#).

4.2 Informed Consent

The investigational nature and objectives of the trial, the procedures and treatments involved and their attendant risks and discomforts, and potential alternative therapies will be carefully explained to the subject and a signed informed consent will be obtained. Documentation of informed consent for screening will be maintained in the subject's research chart and medical record and the patient will receive a copy of the signed informed consent document. All Institutional, Federal, and State regulations concerning Informed Consent will be fulfilled.

4.3 Registration Requirements/Process

Confirming, reserving a slot and dose level assignment

Eligible subjects will be registered on the study centrally by the Data Coordinating Center (DCC) at City of Hope. Staff (including physicians, protocol nurses and/or CRCs) should call the DCC at [contact], [name] to verify the current dose level and slot availability, and to reserve a slot for a specific prospective subject. Slots can only be held for a limited time.

Eligible subjects must be registered **prior** to start of protocol therapy. Issues that would cause treatment delays should be discussed with the Principal Investigator. If a subject does not receive protocol therapy following registration, the subject's registration on the study may be canceled after discussion with the PI. The Data Coordinating Center should be notified of cancellations as soon as possible.

Registration Process

Once a slot at a dose level has been reserved, the signed informed consent has been obtained, all pretreatment evaluations have been performed, and subject's eligibility has been confirmed by the Data Coordinating Center, a subject will be registered on study.

To register a subject, the treating physician should contact the protocol nurse or the responsible Clinical Research Coordinator (CRC) in the Clinical Trial Office (CTO) to complete the eligibility checklist.

The protocol nurse or CRC will contact the Data Coordinating Center at City of Hope [contact], [name] or via e-mail at [contact]), scan and EMAIL a copy of the completed and signed eligibility checklist, a copy of the signed Informed Consent (including a copy of signed subject's bill of Rights and HIPAA authorization form) and copies of any required pre-study test results that are not readily available in the COH electronic medical record to [contact].

The protocol nurse or CRC may then call the Data Coordinating Center [contact] [name]) to confirm receipt of all registration documents. To complete the registration process, the Data Coordinating Center will:

- Verify and confirm the subject's eligibility.
- Assign a subject accession number (for example, COH-001, COH-002, etc.).
- Register the subject on study centrally (the City of Hope CRC assigned to the trial will still be responsible for accessioning via MIDAS).
- Assign the subject to a dose level (as applicable).
- Complete and email a Confirmation of Registration form within 24 hours to include the COH subject study number and dose level to the study team, which will include the Principal Investigator, treating physician, protocol nurse, CRC and COH IDS Pharmacy.
- Call the protocol nurse and/or CRC to verbally confirm registration.
- Enter the subject into Medidata RAVE®.
- A subject failing to meet all protocol requirements will not be registered.

Patients must begin protocol treatment within 1 week following registration date.

4.4 Screen Failures and Registered Participants Who Do Not begin Study Treatment

The reason for screen failure or failure to begin treatment for registered participants will be documented.

5.0 TREATMENT PROGRAM

5.1 Treatment Overview

Treatment on study will be in the outpatient setting and will consist of daily treatment with leflunomide; patients will be treated in planned 28-day treatment cycles. After the decision to end study treatment has been made, participants will receive treatment with cholestyramine ([Section 5.7](#)) to eliminate leflunomide. Participants who end study treatment for reasons other than disease progression will undergo active follow-up ([Section 5.9](#)) until disease progression or the initiation of a new therapy. All participants will be followed for survival ([Section 5.9](#)).

For a detailed tabular view of the treatment, monitoring, and follow-up schedule, see the Study Calendar in [Section 10](#).

5.2 Treatment cycle definition

The planned cycle length is 28 days. Leflunomide will be taken orally once daily. Missed or held doses will not be made up. The day count continues despite a hold in agent administration. Day 1 safety assessments must be reviewed prior to the initiation of the cycle. For a cycle to commence, the participant must be actively taking study agent. Windows for procedures are detailed in [Section 10](#).

5.3 Phase I/II Treatment Plan

This phase I trial will implement a modified rolling six dose escalation, de-escalation, expansion design, a more conservative version of the rolling six design of Skolnik, et al. [1] to ensure safety and to allow for the evaluation of toxicities associated with leflunomide. See [Section 13.3.2](#) for dose escalation/de-escalation/expansion rules, and Section [13.1](#) for the definition of dose limiting toxicity (DLT).

Up to six doses of leflunomide will be considered (see Table 5.3.1). The starting dose of leflunomide is 20mg daily, with the intention to test up to 60mg daily. Escalation will proceed in increments of 20mg/day (odd numbered dose levels); de-escalation will proceed in decrements of 10mg/day. There will be no intra-patient dose escalation; participants will undergo dose modification due to toxicity per [Section 6.2](#).

Table 5.3.1: Dose Levels

Dose Level	Leflunomide Dose*
-1	10 mg PO daily
1	20 mg PO daily
2	30 mg PO daily
3	40 mg PO daily
4	50 mg PO daily
5	60 mg PO daily

*NOTE: Leflunomide is administered with a loading dose of 100 mg for the 1st three doses.

5.4 Phase II Treatment Plan

Following the phase I trial, a single arm phase II study will be conducted using a Simon Two-Stage Optimal Design [2, 3] to evaluate the anti-myeloma activity of leflunomide. For the phase II portion, up to 39 patients will be treated. The six patients treated at the RP2D in the phase I portion of the study will count toward the 39 patients required; given this, we expect to enroll only 33 new patients on the phase II trial.

5.5 Agents Administration

5.5.1 Leflunomide

Participants will be instructed to take each dose of leflunomide orally, once a day, at approximately the same time each day. They may take it with or without food. If a patient forgets or misses a dose for whatever reason, it should **not** be replaced or made up. Participants will be given a study calendar (pill diary) to document each dose of leflunomide that is taken or missed.

NOTE: On study visit days, participants should refrain from taking leflunomide until after blood is collected.

Leflunomide is administered with a loading dose of 100 mg per day for the first three doses (first three days).

There will be no intra-patient dose escalation; patients will undergo dose modification due to toxicity per [Section 6.2](#).

5.5.2 Cholestyramine

Cholestyramine is not a study agent but is required for the elimination of the study agent leflunomide. See [Section 5.7](#) for cholestyramine administration details.

5.6 Study Procedures

For a detailed list of all study procedures including timing and windows, see [Section 10](#).

5.7 End of Treatment Evaluations and Leflunomide Detoxification

All participants will be followed until resolution or stabilization of any serious adverse events occurring during treatment and completion of the Day 30 End of Treatment assessments. See [Section 10](#) for a list of all assessments and windows.

Because of the ability of leflunomide to be reabsorbed through the colon, resulting in a very long half-life, all participants will be treated with cholestyramine to prevent re-absorption of leflunomide after the decision to end study treatment has been made.

Participants removed from study treatment will undergo oral administration of cholestyramine 8 grams oral suspension three times daily for 11 days. It will not be a deviation if an administration of cholestyramine is delayed or if the 11 days are not consecutive. Cholestyramine administration may be adjusted per the discretion of the treating investigator. After the treatment with cholestyramine, clinical laboratory testing will be performed to verify plasma levels less than 0.02 mg/L or 0.02 μ g/mL by two separate tests at least 14 days apart. If plasma levels are higher than 0.02 mg/L or 0.02 μ g/mL, additional cholestyramine treatment will be considered. See [Section 10](#) for a tabular view of cholestyramine administration and metabolite testing windows and days of administration.

Note: Cholestyramine can affect the absorption of other oral medications. Such medications should be taken 1 hour before the first administration or per other guidance in the package insert. Watch for bleeding abnormalities due to vitamin K deficiency for which intravenous vitamin K may be administered.

5.8 Duration of Therapy & Criteria for Removal from Study Treatment

Patients will receive study treatment until disease progression, unacceptable toxicity or other criteria for removal from study treatment are satisfied. Of note, based on the guidelines outlined by Rajkumar et al. [38], “CR patients will need to progress to the same level as VGPR and PR patients to be considered PD. A positive immunofixation alone is therefore not sufficient.” Participants may be removed from treatment for any of the following reasons:

- Evidence of disease progression
- Patient is deemed intolerant to study treatment because of toxicity, despite dose modification/delay
- Intercurrent illness that prevents further administration of treatment
- Participant withdraws from the treatment phase of the study
- General or specific changes in the participant's condition, including non-compliance, which renders the participant unacceptable for further treatment in the opinion of the treating investigator.

Documentation of the reason for discontinuing therapy and the date effective should be made in the medical record and appropriate eCRF. The participant should then proceed to off-treatment procedures for safety monitoring, leflunomide elimination and follow-up procedures. The participant's status is to be modified in the MIDAS system once the off-treatment period is completed. Alternative care options will be discussed with the participant.

5.9 Active Follow Up and Long Term Follow Up

Participants who do not progress while on treatment will be in *Active Follow Up*, where they will continue to undergo monthly response assessment (myeloma labs) until disease progression or the initiation of a new therapy.

Participants who progress during Treatment Phase skip *Active Follow-Up* phase and continue directly into *Long-term Follow-up* phase.

In *Long-term Follow-Up* participants will be followed for survival information which may be obtained by reviewing the City of Hope medical record, contacting the participant and/or a review of outside medical records. Note: this is not intended to be an all-inclusive list.

The schedule and windows for assessments and data collection points are further detailed in Table 10.

5.10 Criteria for Completion of Study Participation

Participants may be removed from the study as a whole at any time at their own request, or they may be withdrawn at the discretion of the investigator for safety, behavioral or administrative reasons. The reason(s) for discontinuing study participation should be documented and may include:

- Participant completes all study procedures including all study follow-up procedures.
- Participant withdraws consent for follow-up.
- Participant is determined to be lost to follow-up. All attempts to contact the subject must be documented.

The reason for study removal and the date the participant was removed must be documented in the source documentation and the study-specific case report form (CRF). The participant's status is to be modified in the MIDAS system once the participant completes the study.

5.11 Supportive Care, Other Concomitant Therapy, Prohibited Medications

Concomitant medications and treatments that are permitted while on study treatment include allopurinol, anti-emetics, anti-diarrheals, FDA-approved bisphosphonates, erythropoietin, transfusions (as necessary), and palliative radiation.

Concurrent treatment with any other anti-neoplastic therapies will not be permitted while on study treatment. Concurrent administration of live vaccines will not be permitted while on study treatment.

During cycle 1 only: Transfusions are not permitted unless platelets <25,000/mm³ or platelets < 50,000/mm³ accompanied by bleeding. Growth factors are not permitted unless ANC <500/mm³.

5.12 Additional Studies

See [Section 9.0](#) for correlative studies.

6.0 ANTICIPATED TOXICITIES AND DOSE DELAYS/MODIFICATIONS FOR ADVERSE EVENTS

6.1 Anticipated Toxicities

6.1.1 Leflunomide

Per the package insert for leflunomide, the expected toxicities for leflunomide follow, where the asterisk (*) signifies a common event (10%-30% of patients), unmarked items are infrequent events (1-3% of patients), a double asterisk (**) signifies a rare but possibly serious event, and a triple asterisk (***+) signifies an event that may become serious and occurs in up to 10% of patients:

Blood and lymphatic system: anemia (including iron deficiency anemia), ecchymosis, pancytopenia**, agranulocytosis**, neutropenia**, thrombocytopenia**, leukopenia**,

Cardiac: angina pectoris, migraine, palpitation, tachycardia, vasodilatation

Endocrine: diabetes mellitus, hyperthyroidism

Eye: blurred vision, cataract, conjunctivitis, eye disorder

Gastrointestinal: diarrhea*, abdominal pain, dyspepsia, nausea, vomiting, oral ulceration, anorexia, pancreatitis**, constipation, esophagitis, flatulence, gastritis, gingivitis, melena, oral moniliasis, pharyngitis, salivary gland enlarged, stomatitis (or aphthous stomatitis), tooth disorder

Hepatobiliary: cirrhosis**, hepatitis**, hepatic failure**, acute hepatic necrosis**, cholelithiasis**, cholestasis**, elevated hepatic enzymes (primarily ALT and AST)

Immune system: allergic reactions, anaphylactoid reactions**

Infections: respiratory infection*, infections (including bronchitis, rhinitis, sinusitis, pharyngitis, pneumonia, and urinary tract infections, oral or vaginal candidiasis, herpes simplex, herpes zoster, and fungal dermatitis), opportunistic and/or severe infections** including sepsis, that may be fatal (especially *Pneumocystis jiroveci* pneumonia, tuberculosis, aspergillosis)

Metabolism and nutrition: hyperglycemia, creatine phosphokinase increased, hyperlipidemia

Musculoskeletal and connective tissue: arthrosis, bone necrosis, bone pain, bursitis, muscle cramps, myalgia, tendon rupture

Neoplasms: secondary malignancy**, cyst

Nervous system: headache*, peripheral neuropathy* (including peripheral numbness, tingling, burning, severe pain, cold sensation in the distal extremities, or extremity weakness), paresthesias, taste perversion (dysgeusia), anxiety, depression, dry mouth, insomnia, neuralgia, neuritis, sleep disorder, sweating increased, vertigo, migraine

Renal and urinary: albuminuria, cystitis, dysuria, hematuria, hypophosphaturia, hyperuricemia, increased urinary frequency

Reproductive: menstrual irregularity/disorder, menstrual disorder, vaginal moniliasis vaginal moniliasis, prostate disorder

Respiratory: interstitial lung disease** (sometimes fatal), interstitial pneumonitis**, pulmonary fibrosis**, asthma, dyspnea, epistaxis, lung disorder

Skin and subcutaneous tissue: maculopapular rash*, dry skin*, alopecia*, hair discoloration*, Stevens-Johnson syndrome**, toxic epidermal necrolysis**, erythema multiforme**, cutaneous lupus erythematosus**, acne, contact dermatitis, fungal dermatitis, hematoma, nail disorder, skin discoloration, skin disorder, skin nodule, subcutaneous nodule, skin ulcer

Vascular: varicose veins, hypertension***, vasculitis, cutaneous necrotizing vasculitis**

Miscellaneous: weight loss*, leg cramps*, jaundice**, allergy related angioedema**, fever, peripheral edema, hernia, neck pain, pelvic pain, pain, abscess, malaise

6.1.2 Cholestyramine

Per the package insert for cholestyramine, the expected toxicities for cholestyramine follow, where the double asterisk (**) signifies a common event, and a single asterisk (*) signifies a less common event, and remaining unmarked items are less likely:

Blood and lymphatic system: anemia, ecchymosis, prolonged prothrombin time, hypoprothrombinemia

Ear and labyrinth: tinnitus, vertigo

Eye: uveitis

Gastrointestinal: constipation**, abdominal pain*, anorexia*, nausea*, vomiting*, diarrhea*, flatulence*, diarrhea*, eructation,* steatorrhea,* diverticulitis, bleeding from known duodenal ulcer, dysphagia, gastrointestinal hemorrhage, hemorrhoidal bleeding,

hiccups, intestinal obstruction (rare), melena, pancreatitis, rectal pain, tongue irritation, tooth enamel damage (dental erosion), dental bleeding, dental caries, dental discoloration

Hepatobiliary: abnormal hepatic function tests, biliary colic, gallbladder calcification,

Immunologic: hypersensitivity reaction

Metabolism: hyperchloremic metabolic acidosis

Musculoskeletal and connective tissue: arthralgia, arthritis, backache, myalgia, osteoporosis associated with vitamin D deficiency

Nervous system: anxiety, dizziness, drowsiness, dysgeusia, fatigue, headache, neuralgia, paresthesia, syncope

Respiratory: asthma dyspnea and wheezing associated with hypersensitivity reaction

Renal and urinary: hematuria, dysuria, burnt odor to urine, diuresis

Skin and subcutaneous tissue: perianal skin irritation, skin irritation, skin rash, urticaria

Miscellaneous: adenopathy, increased libido, edema, bleeding tendencies due to vitamin K deficiency, vitamin deficiency (A, D, E, K), weight loss, weight gain, hematoma, hemorrhage, femoral nerve pain

6.2 Dose Modifications of Leflunomide

6.2.1 General Information

- a. The study will use the NCI Common Terminology Criteria for Adverse Events (CTCAE) version 4.03 to grade toxicities. A copy of the version 4.03 can be downloaded from:
<http://evs.nci.nih.gov/ftp1/CTCAE/About.html>
- b. Intra-patient dose escalation is never permitted in this study. Rules for dose modification are found in Table 6.2.2.
- c. Baseline values are from the last values obtained prior to treatment.
- d. **For holds due to toxicities related to study agent, if the participant does not meet criteria to resume treatment within 14 days, the participant must permanently discontinue study treatment.**

6.2.2 Dose Modifications

The tables below detail the specific dose modifications for toxicities on single agent leflunomide (Table 6.2.2) and are to be used in agreement with the information in [Section 6.2.1](#).

Table 6.2.2 Dose Modifications for Leflunomide Treatment

Adverse Event	Treatment modification
Hematological Toxicities:	
Febrile Neutropenia Grade 3 (ANC: $<1.0 \times 10^9/L$ with a single temperature of $>38.3^{\circ}C$ or a sustained temperature $\geq 38.0^{\circ}C$ for more than one hour.)	Hold study agent. If resolves to $ANC \geq 1.0 \times 10^9/L$ and temperature $< 38.0^{\circ}C$ within 14 days, resume study agent at next lowest safe dose. If does not resolve within 14 days, permanently discontinue study agent.
Febrile Neutropenia Grade 4 Life threatening consequences; urgent intervention needed.	Permanently discontinue study agent.

Neutropenia (ANC) Grade 1 ($1.5 \times 10^9/L < LLN$)	Maintain study agent.
Neutropenia (ANC) Grade 2 ($1.0 - < 1.5 \times 10^9/L$)	Maintain study agent.
Neutropenia (ANC) Grade 3 ($0.5 - < 1.0 \times 10^9/L$)	Maintain study agent. Growth factor recommended after cycle 1.
Neutropenia (ANC) Grade 4 ($< 0.5 \times 10^9/L$)	Hold study agent and provide supportive care. If ANC does not resolve to \leq grade 3 ($ANC \geq 0.5 \times 10^9/L$) in 5 days, permanently discontinue study agent. Otherwise proceed as follows: 
 • If resolves to \leq grade 2 ($ANC \geq 1.0 \times 10^9/L$) in ≤ 14 days, resume study agent at the next lowest safe dose. • If ANC does not resolve to \leq grade 2 ($ANC \geq 1.0 \times 10^9/L$) by 14 days, permanently discontinue study agent.
Thrombocytopenia Grade 1 ($75 \times 10^9/L < LLN$)	Maintain study agent
Thrombocytopenia Grade 2 ($50 - < 75 \times 10^9/L$)	Maintain study agent
Thrombocytopenia Grade 3 without bleeding ($25 - < 50 \times 10^9/L$)	Maintain study agent.
Thrombocytopenia Grade 3 with bleeding ($25 - < 50 \times 10^9/L$)	Hold study agent and provide supportive care. If bleeding does not resolve in 5 days, permanently discontinue study agent. Otherwise proceed as follows: 
 • If bleeding resolves within 5 days and platelets resolve to \leq grade 2 (platelets $\geq 50 \times 10^9/L$) in ≤ 14 days, resume study agent at next lowest safe dose. If bleeding resolves within 5 days but thrombocytopenia does not resolve to \leq grade 2 (platelets $\geq 50 \times 10^9/L$) by 14 days, permanently discontinue study agent.
Thrombocytopenia Grade 4 ($< 25 \times 10^9/L$)	Hold study agent and provide supportive care. If platelets do not resolve to \leq grade 3 (platelets $\geq 25 \times 10^9/L$) in 5 days, permanently discontinue study agent. Otherwise proceed as follows: 
 • If resolves to \leq grade 2 (platelets $\geq 50 \times 10^9/L$) in ≤ 14 days, resume study agent at next lowest safe dose. • If thrombocytopenia does not resolve to \leq grade 2 (platelets $\geq 50 \times 10^9/L$) by 14 days, permanently discontinue study agent.
Gastrointestinal	
Diarrhea Grade 1 (2-3 stools/day $>$ baseline)	Maintain treatment.
Diarrhea Grade 2 (4-6 stools/day $>$ baseline)	Maintain study agent.
Diarrhea Grade 3 (7-9 stools/day $>$ baseline)	Hold study agent and provide optimal anti-diarrheal therapy. First Occurrence: If resolves to \leq grade 1 in ≤ 7 days, resume at pre-hold dose. If resolves to \leq grade 1 in 8-14 days, resume study agent at next lowest safe dose. If does not resolve within 14 days, permanently discontinue study agent. Recurrence: If resolves to \leq grade 1 in ≤ 14 days, resume at next lowest safe dose. If does not resolve within 14 days, permanently discontinue study agent.

Diarrhea Grade 4 (≥10 stools/day > baseline)	
Hold study agent and provide optimal anti-diarrheal therapy.
 
If does not resolve to Grade 3 within 48 hours, permanently discontinue study agent.
 
If resolves to Grade 3 within 48 hours, then:
 
First Occurrence:
 
 Hold until resolution to ≤ grade 1. If resolved in ≤ 7 days, resume at pre-hold dose. If resolved in 8-14 days, resume study agent at next lowest safe dose. If not resolved within 14 days, permanently discontinue study agent. 
Recurrence:
 
 Hold until resolution to ≤ grade 1. If resolved in ≤ 14 days, resume study agent at next lowest safe dose. If not resolved within 14 days, permanently discontinue study agent.
Vomiting or Nausea Grade 1	Maintain study agent.
Vomiting or Nausea Grade 2	Maintain study agent.
Vomiting or Nausea Grade 3	
Hold study agent and provide optimal supportive care/therapy.
 
First Occurrence:
 
 If resolves to ≤ grade 1 in ≤ 7 days, resume at pre-hold dose. If resolves to ≤ grade 1 in 8-14 days, resume study agent at next lowest safe dose. If does not resolve within 14 days, permanently discontinue study agent. 
Recurrence:
 
 If resolves to ≤ grade 1 in ≤ 14 days, resume at next lowest safe dose. If does not resolve within 14 days, permanently discontinue study agent.
Vomiting Grade 4	
Hold study agent and provide optimal supportive care/therapy.
 
If does not resolve to Grade 3 within 48 hours, permanently discontinue study agent.
 
If resolves to Grade 3 within 48 hours, then:
 
First Occurrence:
 
 Hold until resolution to ≤ grade 1. If resolved in ≤ 7 days, resume at pre-hold dose. If resolved in 8-14 days, resume study agent at next lowest safe dose. If not resolved within 14 days, permanently discontinue study agent. 
Recurrence:
 
 Hold until resolution to ≤ grade 1. If resolved in ≤ 14 days, resume study agent at next lowest safe dose If not resolved within 14 days, permanently discontinue study agent.
Hepatic investigations	
ALT (SGPT) or AST (SGOT) ≤ 3.0 x ULN or TBili ≤ 1.5 x ULN	Maintain study agent.
ALT (SGPT) or AST (SGOT) >3.0 - 5.0 x ULN or TBili >1.5 - ≥ 3.0 x ULN	
First Occurrence:
 
 Hold until resolution to < 3.0 x ULN for ALT or AST or < 1.5 for TBili. Resume at pre-hold dose if resolved within 14 days. If does not resolve within 14 days, permanently discontinue study agent. 
Recurrence:
 
 Hold until resolution to < 3.0 x ULN for ALT or AST or < 1.5 for TBili. Resume at next lowest safe dose if resolved within 14 days. If does not resolve within 14 days, permanently discontinue study agent.
ALT (SGPT) or AST (SGOT) > 5.0 x ULN or TBili > 3.0 x ULN	Permanently discontinue study agent.
Electrolyte/metabolic toxicity	

Electrolyte/metabolic Grade 3	Provide support care. Maintain study agent per investigator discretion. If alteration persists despite aggressive replacement therapy, then dose reduce or permanently discontinue (per investigator discretion with PI consultation).
Electrolyte/metabolic Grade 4	Provide support care. Maintain study agent per investigator discretion. If resolves to Grade 1 or baseline within 48: for first event, maintain at pre-hold dose; for recurrent event, dose reduce or permanently discontinue (per investigator discretion with PI consultation). If does not resolve to Grade 1 or baseline within 48 hours, permanently discontinue study agent.
Other unspecified Non-Hem toxicities considered related to leflunomide	
Grade 1	Maintain study agent.
Grade 2	Maintain study agent.
Grade 3	First Occurrence: Hold until resolution to ≤ Grade 2. Resume at pre-hold dose if resolved within 7 days. If does not resolve within 7 days, permanently discontinue study agent. Recurrence: Hold until resolution to ≤ Grade 1. Resume at next lowest safe dose if resolved within 14 days. If does not resolve within 14 days, permanently discontinue study agent.
Grade 4	Permanently discontinue study agent.
Other unspecified Non-Hem Toxicities considered UNRELATED to study agent	
Other unspecified events of any grade considered unlikely to be related or not related to study agents.	Maintain treatment with study agents. Interruption of study agent or dose de-escalation is permitted if the investigator consults with the Principal Investigator to determine that this is in the best interest of the participant.

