The long half-life of the metabolite (about 2 weeks) affects management of patients taking leflunomide. A loading dose of 100 mg for 3 days is used to facilitate rapid attainment of steady state levels of M1. Without a loading dose, it is estimated that attainment of steady state concentrations would require nearly two months of dosing [22]. To eliminate the metabolite, a drug elimination procedure using cholestyramine is recommended. Cholestyramine, a bile acid sequestrant, fixes the metabolite, preventing reabsorption and expediting drug elimination. Without the drug elimination procedure, it may take up to 2 years to reach non-detectable plasma levels after stopping treatment with leflunomide [22].

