3.0 PATIENT ELIGIBILITY

3.1 Inclusion Criteria

Participants must meet the following criteria on screening examination to be eligible to participate in the study:

Patient MRN:	Patient Initials (F, M, L):
--------------	-----------------------------

Informed Consent

1. All subjects must have the ability to understand and the willingness to sign a written informed consent.

Age Criteria, Performance Status, and Life Expectancy

2. Patients must be age \geq 18 years.

3. Patients must have a life expectancy of > 3 months.

4. Patients must exhibit an ECOG performance status of 0-2.

Nature of Illness and Treatment History

5. Patients must have a diagnosis of multiple myeloma.

6. Patients must have measurable disease, defined as one of the following within 21 days prior to registration:

- Serum M-protein ≥ 0.5 g/dL
- Urine M-protein ≥ 200 mg/24 hr
- Serum free light chain ≥ 10 mg/dL provided the FLC ratio is abnormal.
- 10% plasma cells in bone marrow

7. Patients must be relapsed or are refractory to at least 3 prior lines of therapy, including both a proteasome inhibitor and an IMiD, and for whom transplant is not recommended (induction therapy and stem cell transplant +/- maintenance will be considered as one regimen).

8. At least 2 weeks from prior therapy to time of start of treatment. Prior therapy includes steroids (except prednisone or equivalent – up to 10 mg per day is allowed).

Clinical laboratory parameters

9. Platelet count $\geq 50,000/\mu\text{L}$. Platelet transfusions are not allowed within 14 days of platelet assessment.

10. ANC $\geq 1000/\text{mm}^3$. Growth factor is not permitted within 14 days of neutrophil assessment.

11. AST and ALT $< 2.0 \times \text{ULN}$.

12. Total Bilirubin $< 1.5 \times \text{ULN}$.

13. Calculated creatinine clearance (CrCl) ≥ 30 mL/min per 24-hour urine collection or the Cockcroft-Gault formula.

$$\text{CrCl (mL/min)} = \frac{(140-\text{age}) \times \text{actual body weight (kg)}}{72 \times \text{serum creatinine (mg/dL)}} \quad (\times 0.85 \text{ for females})$$

Or

$$\text{CrCl (mL/min)} = \frac{(140-\text{age}) \times \text{actual body weight (kg)}}{0.8136 \times \text{serum creatinine (umol/L)}} \quad (\times 0.85 \text{ for females})$$

- 14. Negative serum or urine β -HCG test (female patient of childbearing potential* only), to be performed locally within the screening period.
- 15. Negative for tuberculosis antigen (e.g. T-Spot test).
- 16. Negative for hepatitis A, B, or C infection.

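### Table 6.2.2, liver rows: with more than one raised test, the resume line can be met while the hold row still applies, and the bilirubin hold band as it reads overlaps the discontinue row

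*Combined protocol and SAP*

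**What the plan says.** Table 6.2.2 (Section 6.2.2) has three liver rows, each joining the tests with *or*.

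- **Maintain:** ALT or AST at or below 3.0 x ULN, or bilirubin at or below 1.5 x ULN.
- **Hold:** "ALT (SGPT) or AST (SGOT) >3.0 - 5.0 x ULN or TBili >1.5 - ≥ 3.0 x ULN".
- **Permanently discontinue:** "ALT (SGPT) or AST (SGOT) > 5.0 x ULN or TBili > 3.0 x ULN".

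Within the hold row, the first-occurrence and recurrence lines carry the same resume condition: "Hold until resolution to < 3.0 x ULN for ALT or AST or < 1.5 for TBili". If it is met within 14 days, a first occurrence restarts at the pre-hold dose and a recurrence at the next lowest safe dose. If not, leflunomide stops for good. Section 6.2.1, item d, repeats the limit for all holds due to related toxicity: "if the participant does not meet criteria to resume treatment within 14 days, the participant must permanently discontinue study treatment". That item relies on the resume criteria and does not define them.

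Neither Section 6.2.1 nor the DLT definition in Section 13.1 says how to read the rows when more than one liver test is raised.

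**The concern.** The resume line decides between restarting and stopping for good, so it should give one answer per patient. With several raised tests it can give two: the line is literally satisfied by the test that has recovered, while the test still raised puts the patient back in the row that says hold.

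The bilirubin hold band adds a second conflict. As it reads, its upper end carries ≥ where ≤ would be expected, so the band has no effective ceiling and runs into the discontinue row.

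Section 6.1.1 lists hepatic failure and acute hepatic necrosis among the rare but possibly serious toxicities. A restart with one liver test still raised is the error that these rows exist to prevent.

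**Working it through.** The plan gives no figure to reproduce here. The check applies the rows to example patients, with all values in multiples of ULN.

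**Inputs (Table 6.2.2)**
- Hold: ALT or AST > 3.0 to 5.0, or bilirubin > 1.5 up to the band's upper end.
- Resume, literal: at least one test raised at the start of the hold is back below its limit (ALT or AST < 3.0, bilirubin < 1.5).
- Resume, all: ALT < 3.0 and AST < 3.0 and bilirubin < 1.5.
- Discontinue: ALT or AST > 5.0, or bilirubin > 3.0.

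**Step 1: resume line against hold row.** Tests not mentioned are taken as normal.

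| Raised at start of hold | Values at re-test | Hold row met? | Resume, literal | Resume, all |
|---|---|---|---|---|
| ALT, bilirubin | ALT 2.5, bilirubin 2.8 | yes (bilirubin) | yes | no |
| ALT, bilirubin | ALT 4.0, bilirubin 1.2 | yes (ALT) | yes | no |
| ALT, AST | ALT 2.5, AST 4.0, bilirubin 1.0 | yes (AST) | yes | no |
| ALT, bilirubin | ALT 2.5, bilirubin 1.2 | no | yes | yes |

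The first three rows conflict. Take the first at day 14 of a first hold. The literal resume line restarts the pre-hold dose. The hold row still applies, and if every raised test must recover, the 14-day limit means permanent discontinuation.

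Under the *all* version no conflict is possible. Resuming needs ALT and AST below 3.0 and bilirubin below 1.5, while the hold row needs at least one of them above those values.

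**Step 2: bilirubin band.**

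| Bilirubin | Rows met, band as it reads | Rows met, band ending ≤ 3.0 |
|---|---|---|
| 3.0 | hold | hold |
| 3.5 | hold and discontinue | discontinue |
| 4.0 | hold and discontinue | discontinue |

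**Step 3: maintain row.** ALT 4.0 with normal bilirubin literally meets both the maintain row (through bilirubin) and the hold row (through ALT). Letting the most severe row govern gives hold.

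**Step 4: what the documents suggest was meant.** Elsewhere Table 6.2.2 uses *and* when two things must both recover: neutrophils and temperature after febrile neutropenia, and bleeding and platelets after grade 3 thrombocytopenia with bleeding. Section 3.1 requires AST and ALT < 2.0 x ULN and, separately, bilirubin < 1.5 x ULN, and both must be met. The likely intent is therefore that every raised test recovers.

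**Step 5: link to DLT.** Section 13.1 counts fewer than 21 doses in cycle 1 as a DLT if caused by toxicity at least possibly related to leflunomide. Section 5.2 says held doses are not made up. In a 28-day cycle:
- 7 days held: 28 − 7 = 21 doses, not a DLT on this criterion.
- 8 days held: 28 − 8 = 20 doses, a DLT.

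Suppose a cycle 1 hold begins on day 15, after 14 doses. ALT is below its limit after 7 held days, but bilirubin needs 8. The literal line restarts on day 22 and gives 14 + 7 = 21 doses. The *all* version restarts on day 23 and gives 14 + 6 = 20. If the event is related, every other dose is taken and no other DLT criterion is met, the reading alone decides whether a DLT is counted.

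**The case against.** The best defence is that the rows are meant to be read test by test, each against its own limit. Read literally throughout, the maintain row would keep a patient with very high ALT and normal bilirubin on drug, which nobody intends. The resume line also speaks of resolution, and a liver toxicity with bilirubin at 2.8 x ULN has not resolved. The line needs context anyway, since it omits x ULN after the bilirubin limit.

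There are safeguards too. Day 1 safety results must be reviewed before each cycle, tests may be added when clinically indicated, the trial has a single centre, and Section 12.2.3 tells the pharmacy to take ambiguities to the Principal Investigator. For bilirubin above 3.0 x ULN the discontinue row is explicit and stricter, and the odd sign may come from reading the PDF.

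Much of this stands. A careful clinician would probably require each raised test to recover. But that reading is not written down, and referral to the Principal Investigator settles cases one at a time rather than supplying a rule.

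Two stronger inferences are not supported. A reader might infer that the plan orders an early restart; it does not, because the hold row still applies to the remaining test. A reader might also take the drug's persistence as the size of the harm. Section 2.2 notes "The long half-life of the metabolite (about 2 weeks) affects management of patients taking leflunomide", and Section 5.7 says "all participants will be treated with cholestyramine to prevent re-absorption of leflunomide after the decision to end study treatment has been made", so a restart after a hold does not begin from a washed-out state. But that is true after a hold for any toxicity and under any wording of this line, so it does not measure this defect.

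**Conclusion.** The point holds as a minor safety-wording correction. With more than one raised liver test, Table 6.2.2 as written can tell the same patient both to restart and to stay on hold, or to stop for good at 14 days. The bilirubin overlap holds only on the text as it reads and depends on checking one sign; the resume-line point does not depend on it.

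The documents do not say how often several liver tests rise together, so no number of patients can be given. A reader might infer that a wording slip in a dose table cannot touch the trial's results. That goes too far for phase I: in cycle 1 the reading can move a related event across the 21-dose line and so change a DLT count. Sample size, error rates and the rules for the ORR analysis are unaffected. The strict resume limits are not in question; the bilirubin limit, taken as x ULN, equals the entry limit.

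**What to change.** At the next amendment, in Table 6.2.2:

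1. In both the first-occurrence and recurrence lines, write: hold until ALT and AST are < 3.0 x ULN and TBili is < 1.5 x ULN (all of them).
2. After checking the source, print the bilirubin hold band as > 1.5 - ≤ 3.0 x ULN.
3. Add one line: the most severe row met by any liver test governs. This also repairs the maintain row.

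The cost is a few words of table text. The downside is that a few patients with several raised tests stay on hold longer or discontinue, and in cycle 1 a longer hold may leave fewer than 21 doses and so count as a DLT if related.
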